7.3.7. Survey of Autonomic Symptoms (SAS)

The Survey of Autonomic Symptoms (SAS) is a validated, easily administered instrument to measure autonomic symptoms that has been proposed to be valuable in assessing neuropathic autonomic symptoms in clinical trials (refer to [Appendix 15](#)).

Subjects will complete the SAS at Screening, prior to SC dosing at Weeks 24, 56 and 80 (or at Early Termination Visits 1 and 3). Subjects will enter responses in IRT.

7.3.8. Radiographic Assessments

A central radiology reader (Central Reader) will review the radiology images for assessment of eligibility including determination and identification of exclusionary joint conditions such as rapidly progressive osteoarthritis, atrophic or hypotrophic osteoarthritis, subchondral insufficiency fractures, spontaneous osteonecrosis of the knee (SPONK), primary osteonecrosis, or pathological fractures.

During the study, the Central Reader will review radiology images for continued radiologic eligibility and for diagnosis of joint conditions that would warrant further evaluation by the Adjudication Committee such as rapidly progressive osteoarthritis, subchondral insufficiency fractures, spontaneous osteonecrosis of the knee (SPONK), primary osteonecrosis, or pathological fracture.

Central Readers will be board certified radiologists or have the international equivalent as musculoskeletal radiologists. The Central Readers will be governed by an imaging atlas and an imaging Charter which includes a specific description of the scope of their responsibilities.

The X-ray technologists, in addition to their professional training and certifications, will be trained in performing the radiographic protocols for the hips, knees, and shoulders for this study and given approval by Pfizer or its representative to perform study X-rays. To facilitate reproducibility and accuracy of joint space width measurement in the knees and hips, a standardized subject and joint positioning protocol will be utilized. The Core Imaging Laboratory will be responsible for working with the sites to ensure quality, standardization and reproducibility of the radiographic images/assessments made at the Screening and follow-up time-points. Additional details regarding the required X-rays will be provided in a site imaging manual.

Radiographic assessments (X-rays) of the hips, knees and shoulders will be obtained at Screening, Weeks 24, 56 and 80 (or at Early Termination Visit 1 and 3). Other major joints exhibiting signs or symptoms suggestive of osteoarthritis should also be imaged. A major joint is defined as a mobile synovial joint in the limbs such as shoulders, elbows, wrists, hips, knees, ankles and excluding the joints of the toes and hands. Any joint imaged at Screening or other at-risk joints identified during the study period should also be imaged at the same intervals as the knees, hips, and shoulders.

It is recommended that the radiographs required at Screening be obtained at least two weeks prior to the Baseline visit to permit central radiology review of the images and to establish

subject eligibility for initial dosing in the study. Subjects will not be permitted to start dosing in the study until the Screening radiographs are reviewed by the Central Reader and eligibility is established. Radiographs required for the Week 24 visit may be conducted up to 30 days before the visit, but it is recommended that the Week 24 radiographs be obtained at least two weeks prior to the Week 24 visit to permit Central Reader review of the images and to establish eligibility for continuation in the study. Radiographs required for the Week 56 visit may be conducted within 30 days of the visit (ie, before or after the visit). The window for the Week 80 X-rays is ± 30 days of the nominal time of the visit but should be obtained as close as possible to the Week 80 visit, and preferably no more than 14 days after the Week 80 visit.

The Central Reader will review the Week 24 knee X-rays to confirm continued radiologic eligibility and for evidence of radiographic progression of knee osteoarthritis. The Central Reader will identify subjects entering the study with asymptomatic knee osteoarthritis Kellgren Lawrence Grade 2 who progress to Kellgren Lawrence Grade ≥ 3 at Week 24. These subjects should be discontinued from tanezumab treatment and entered into the Early Termination Follow-up. The images from these patients will not be reviewed by the Adjudication Committee unless the Central Reader determines the subject has developed a joint condition that would require evaluation by the Adjudication Committee such as rapidly progressive osteoarthritis, subchondral insufficiency fractures, spontaneous osteonecrosis of the knee (SPONK), primary osteonecrosis or, pathological fracture.

For subjects discontinued prior to the Week 56 visit, follow-up radiographs of the hips, knees and shoulders should be performed as soon as possible (refer to Section 6.9.1) after the decision to withdraw from the study has been made, provided at least 30 days have passed since the last set of X-rays were collected. A final set of follow-up radiographs of the hips, knees and shoulders should be obtained 24 weeks (Early Termination Visit 3, Section 6.9.1.5) after the last dose of SC investigational product was administered. Any joint imaged at Screening or other at risk joints identified during the study period should also be imaged at Early Termination Visits 1 and 3.

For subjects who are identified by the Central Readers as having a possible or probable joint event (ie, rapidly progressive osteoarthritis, subchondral insufficiency fractures, spontaneous osteonecrosis of the knee [SPONK], primary osteonecrosis, or pathological fracture) and for subjects undergoing total joint replacement for any reason, all images and other source documentation will be provided to the blinded tanezumab Adjudication Committee for review and adjudication of the event. The Adjudication Committee's assessment of the event will represent the final classification of the event.

7.3.8.1. Radiation Exposure

The International Commission on Radiation Protection (ICRP) has developed and applied the ALARA principle in developing guidelines that balance the benefits of radiation exposures against possible risks. This principle states that human exposures to radiation should be "As Low As Reasonably Achievable, with economic and social considerations taken into account."

Within the context of medical and research exposures, this is usually taken to mean that each individual should receive no more radiation than is necessary to obtain reliable information and that no more research participants should be irradiated than is necessary to answer a particular scientific question.

Radiograph	Annual Effective Dose (mSv)
Knee	0.024 mSV
Hip	1.9 mSV
Shoulder	0.04 mSV
Total	1.964 mSV

The average annual subject exposure per body part imaged is shown in the table above.^{25,26} The annual total effective dose per subject in this study is expected to be approximately 2.0 mSv. This can be compared to the annual effective dose from natural background radiation of approximately 3.0 mSv. In some cases, it is expected that a repeat image of a joint may necessary due to the quality of the X-ray images.

7.3.9. Neurologic Examination

Neurologic examinations will be performed by the investigator or designated physician and assessed for clinically significant changes from Baseline. The examinations will be performed at Screening, Baseline, and Weeks 2, 4, 8, 16, 24, 32, 40, 48, 56, 64 and 80 (or at Early Termination) and the Neuropathy Impairment Score (NIS) will be completed at these time points based on this neurological exam (refer to [Appendix 7](#)). Neurologic examination will assess strength of groups of muscles of the head and neck, upper limbs and lower limbs, deep tendon reflexes and sensation (tactile, vibration, joint position sense and pin prick) of index fingers and great toes in order to complete the NIS. The NIS is a standardized instrument which has been tested in both healthy subjects and patients with neuropathy and which has been used to evaluate subjects for signs of peripheral neuropathy in clinical trials.²⁷ Investigators and other designated physicians performing the neurologic examination are required to attend a training session for neurological exam in order to apply consistency across sites. The neurological exams must be performed in a controlled and consistent manner and by the same examiner when possible.

A neurologic evaluation should be performed by a consulting neurologist if any of the following occurs:

- If an adverse event suggestive of new or worsening peripheral neuropathy or an adverse event of abnormal peripheral sensation (eg, allodynia, burning sensation, carpal tunnel syndrome, dysesthesia, hyperesthesia, hyperpathia, hypoesthesia, neuralgia, neuritis, neuropathy peripheral, pallesthesia, paresthesia, peripheral sensory neuropathy, sciatica, sensory disturbance, sensory loss, tarsal tunnel syndrome) reported as: 1) a serious adverse event or 2) an adverse event which has resulted in the subject being withdrawn from the study, or 3) an adverse event ongoing at the end of the subject's participation in the study, or 4) an adverse event of severe intensity.

- A new or worsened clinically significant abnormality on the neurologic exam should be reported as an adverse event and may result in a neurologic evaluation/consult further to the guidance above.
- A neurological adverse event which is non-neuropathic (eg, stroke, seizure) but which the investigator considers medically important should also result in a neurological consultation.

In these cases, a neurologic evaluation should be obtained as soon as possible after these signs and symptoms are known. The results of the neurological consultation will be recorded on the appropriate CRF and adverse event (if applicable) forms. Adverse events will be reported where applicable as described in Section 8.

7.3.10. Anti-Drug Antibody Testing

7.3.10.1. Serum for Analysis of Anti-Drug Antibodies (ADA) Against Tanezumab

Blood samples for the assessment of ADA against tanezumab (anti-tanezumab antibodies) will be collected at Baseline (Day 1; pre-dose) and Weeks 8 (pre-dose), 16 (pre-dose), 32 (pre-dose), 48 (pre-dose), 56, 64 and 80. If subjects terminate prior to Week 56, ADA will be determined at approximately 8, 16 and 24 weeks after the last SC investigational product was administered (or at Early Termination).

Instructions regarding sample processing (eg, sample volumes, tube types, storage temperatures) will be provided in the laboratory manual.

Samples will be analyzed using a validated analytical method in compliance with Pfizer Standard Operating Procedures.

Samples may be used for further evaluation of the bioanalytical method. These data will be used for internal exploratory purposes and will not be included in the clinical report.

The shipment address and assay lab contact information will be provided to the investigator site prior to initiation of the trial.

7.4. Triggered Requirements and Subject Level Stopping Rules

The following rules will apply to individual subjects at the time of the second and subsequent injections of SC investigational product.

7.4.1. Dysesthesia/Allodynia

Transient, resolved dysesthesia/allodynia: Administer SC investigational product as planned as long as the condition has resolved before the next scheduled dose of investigational product.

Unresolved dysesthesia/allodynia: Withhold the SC investigational product for a maximum of 14 days beyond the planned dosing day to allow for resolution of the adverse event. If the dysesthesia/allodynia has not resolved within the 14-day period after the scheduled dosing

date, the subject will not receive any additional doses of investigational product and will enter the Early Termination Follow-up Period (see Section 6.9).

7.4.2. Hypersensitivity or Injection Site Reactions

If a severe hypersensitivity reaction or severe injection reaction occurs following any administration of SC investigational product, the investigational product should be discontinued immediately and no further administrations of SC investigational product will be allowed. Subjects experiencing these types of reactions will enter the Early Termination Follow-up Period (see Section 6.9).

Severe hypersensitivity reactions are defined as those causing anaphylaxis. Severe injection site reactions are defined as those in which ulceration or severe necrosis occurs.

7.4.3. Orthostatic Hypotension and Sympathetic Function Adverse Events

Blood pressure changes meeting the pre-specified criteria for orthostatic hypotension and confirmed as described in Section 7.3.5.1 will be designated as confirmed orthostatic hypotension episode and should be reported as an adverse event whether or not the subject had accompanying symptoms.

Confirmed episodes of orthostatic hypotension: If a confirmed episode of orthostatic hypotension occurs (as defined in Section 7.3.5.1) it should be reported as an adverse event and the subject should be further evaluated as described below to determine if a neurology or cardiology consultation should be obtained and/or whether further treatment with investigational product should occur. Figure 6 provides a flow diagram for the processes described below.

1. If no apparent medical cause (eg, dehydration, illness, medications) is identified at the time the orthostatic hypotension criterion is met and the subject is symptomatic, the subject should be further evaluated for the presence of sympathetic autonomic neuropathy by a cardiologist or neurologist as soon as possible. See “Sympathetic function adverse events” below for decisions regarding subject management and continued dosing with investigational product.
2. If an apparent medical cause is identified at the time the orthostatic hypotension criterion is met or if subject is asymptomatic, the subject should have a repeat assessment of orthostatic hypotension performed at least 1 week later but not more than 4 weeks later. During this time the investigator should attempt to address the underlying medical cause of the orthostatic hypotension. If confirmed orthostatic hypotension (as defined in Section 7.3.5.1) is present at the follow-up visit, the subject should be further evaluated for the presence of sympathetic autonomic neuropathy by a cardiologist or neurologist as soon as possible. See “Sympathetic function adverse events” below for decisions regarding subject management and repeat dosing.

[figure not shown]
Sympathetic function adverse events: Subjects reporting adverse events (any seriousness or severity) with preferred terms of bradycardia (see Section 7.3.6 for ECG criteria for

bradycardia), syncope, orthostatic hypotension (as described above and in boxes C and E of flow diagram [Figure 6](#)), anhidrosis or hypohidrosis should be further evaluated for the presence of sympathetic autonomic neuropathy by a cardiologist or neurologist as soon as possible.

The investigator should determine the appropriate type of consultation (neurology or cardiology) depending on the subject's symptom presentation and the investigator's assessment as to the specialist best able to evaluate the subject. Pfizer will provide a guidance document which outlines appropriate recommendations regarding tests to consider for subject work-up.

These subjects should not be dosed with SC investigational product until the absence of sympathetic autonomic neuropathy has been confirmed. Subjects who are not deemed to have a sympathetic autonomic neuropathy based on this evaluation can continue the study provided no more than 12 weeks have elapsed since the last dose of SC treatment (Boxes H and K of flow diagram [Figure 6](#)). However, if the subject is still symptomatic with bradycardia, syncope, orthostatic hypotension, anhidrosis or hypohidrosis up to 12 weeks after the last dose of SC treatment, he/she should not receive additional investigational product; even if a sympathetic autonomic neuropathy has not been confirmed (Boxes J and L of flow diagram [Figure 6](#)), and will enter the Early Termination Follow-up Period (refer to [Section 6.9](#)). Subjects found to have a sympathetic autonomic neuropathy (Boxes I and L of flow diagram [Figure 6](#)), should not receive additional investigational product and will enter the Early Termination Follow-up Period (see [Section 6.9](#)).

Figure 6. Follow-up Procedures for Confirmed Orthostatic Hypotension Events

OH=Orthostatic Hypotension

7.4.4. Evaluation and Follow-up for Increased, Severe Persistent Joint Pain

On a weekly basis beginning at the IPAP and through Week 80 of the study, the subject will be asked via the IRT if he/she experienced new onset or increased pain in a major joint (refer to Section 7.3.2). If a subject responds that he/she has experienced new onset or increased pain in a major joint (post-baseline), the subject will be asked to rate his/her pain in that joint on the same 11-point numeric rating scale, using a 24-hour recall and will be asked to rate his/her pain in that joint for the remainder of the study.

Joint pain scores recorded electronically will be monitored by site staff to identify subjects who have a pattern of severe pain over several days or a rapid increase in pain. Subjects who record increased pain scores of severe intensity (score of 7-10 out of 10 on a numerical rating scale) in a knee, hip, shoulder, or other major joint which is persistent for at least 2 weeks despite treatment with analgesic medication should be evaluated by the investigator to determine the source of the subject's pain and whether more comprehensive evaluation (e.g., radiographic or MRI imaging, orthopedic consultation) of the subject is warranted. An earlier evaluation of the subject can be made at the discretion of the investigator.

At each study visit, systematic site review of the joint pain scores and relevant spontaneously reported adverse events will be implemented. In addition, adverse events of joint pain, joint swelling, joint injury/accidents, fractures or osteoarthritis symptoms will be evaluated by the site personnel. An assessment of the subjects' general health and major joints for any changes in their joint status will be carried out.

Musculoskeletal physical exam findings, review of reported musculoskeletal adverse events, and in-clinic efficacy assessments will be recorded on specific case report forms for each study visit.

Subjects meeting the criteria for increased severe or persistent pain or with other clinically significant findings based on the assessment of the investigator are considered to have a joint(s) at risk and must have radiographs (X-rays) of the joint(s) obtained and sent to the Central Reader for assessment. Magnetic Resonance Imaging (MRI) scans will not be required but may be obtained if warranted for diagnostic purposes. If warranted, the subject should be referred to an orthopedic surgeon for evaluation.

Radiographic and any MRI images collected as part of follow-up procedures for reports of increased severe or persistent pain or clinically significant findings of the investigator will be assessed by the Central Reader for possible or probable events of rapidly progressive osteoarthritis, subchondral insufficiency fractures (spontaneous osteonecrosis of the knee [SPONK]), primary osteonecrosis, or pathological fracture (Refer to Sections 7.4.5 and 9.5).

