	Week 60	Week 64	Week 68, 72, 76	Week 80 End of Study	ET Visit 1	ET Telephone Contact 1	ET Visit 2	ET Telephone Contact 2	ET Visit 3
Study Activities	(±7 days) Telephone Contact	Day 449 (±7 days)	(±7 days) Telephone Contact	Day 560 (±7 days)	8 weeks after last dose of SC Study Med (±7 days)	12 weeks after last dose of SC Study Med (±7 days)	16 Weeks after last dose of SC Study Med (±7 days)	20 weeks after last dose of SC Study Med (±7 days)	24 Weeks after last dose of SC Study Med (±7 days)
Trial Treatment									
Dispense rescue medication		X			X		X		
Assign standard of care treatment as needed		X					X		

Abbreviations: → = Ongoing/Continuous event; BMI = body mass index; BP = Blood Pressure; BPI-sf = Brief Pain Inventory-Short Form, ECG = Electrocardiogram; EQ-5D-5L = EuroQol 5 Dimension ; FSH = Follicle Stimulating Hormone; HCRU = Health Care Resource Utilization; HIV = Human Immunodeficiency Virus; HR = Heart Rate; IPAP = Initial Pain Assessment Period; IRT = Interactive Response Technology; LBPI = Low Back Pain Intensity; mPRTI = Patient Reported Treatment Impact assessment-modified; NGF = Nerve Growth Factor; NIS = Neuropathy Impairment Score; NSAID = Non-Steroidal Anti-Inflammatory Drug; PD = Pharmacodynamics; PK = Pharmacokinetic; RMDQ = Roland-Morris Disability Questionnaire; SAS = Survey of Autonomic Symptoms; SC = Subcutaneous; SC = Screening; TSQM (v.II) = Treatment Satisfaction Questionnaire Medicine version II; WPAI:LBP = Work Productivity and Activity Impairment Questionnaire: Low Back Pain

- a. All study activities at Baseline (Day 1), Weeks 8, 16, 24, 32, 40 and 48 should be performed prior to dosing with investigational product, unless otherwise noted.
- b. Telephone Contact Visit: Contact subject and review adverse events (including any new or persistent joint pain, joint procedures or surgeries), compliance with contraceptive requirements, concomitant medications and concomitant use of analgesics for chronic low back pain, as appropriate. If adverse events dictate that the subject should be seen, an unscheduled visit may be conducted and pertinent exams conducted (eg, physical exam, neurological exam, ECG, clinical laboratory testing) depending on the nature of the event and the investigator’s clinical judgment.
- c. A neurological examination (NIS) will be performed by the investigator (or designated physician) and assessed for clinically significant changes from Baseline.
- d. BPI-sf to be conducted at Week 40 only.

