7.3.1.2. Musculoskeletal History and Physical Examination

Each subject will also undergo a musculoskeletal physical examination at Screening, Baseline, Weeks 2, 4, 8, 16, 24, 32, 40, 48, 56, 64 and 80 (or Early Termination Visits). At Screening, the investigator should collect a thorough musculoskeletal history. The investigator should inquire about current and past history of osteoarthritis, ligament tear or rupture, joint surgeries (including arthroscopic procedures), fractures, gout, osteoporosis, or osteopenia, joint injuries, or other conditions.

At each visit, the Investigator will conduct a thorough musculoskeletal physical examination of all major joints. The musculoskeletal physical exam should evaluate the joints for swelling, redness, tenderness, deformity, osteophytes or nodes, crepitus and range of motion and will be documented on the CRF. The Investigator should also collect subject-reported information on any current joint symptoms including pain, stiffness, and swelling. Any clinically significant change in symptoms or the examination should be reported as an adverse event.

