7.4.5. Central Reader and Subject-Level Stopping Criteria for Joint Safety Events

Subjects identified through the measures described above (in Section 7.4.4) who are determined by the Central Reader to have possible or probable joint safety event (rapidly progressive osteoarthritis [type-1 or type-2]), subchondral insufficiency fractures (spontaneous osteonecrosis of the knee [SPONK]), primary osteonecrosis, or pathological

fracture will be withdrawn from treatment and enter the Early Termination Follow-up period (see [Section 6.9](#)).

The Central Reader will review the radiology images on an ongoing basis and provide assessments to the investigator and Pfizer. For subjects who are identified with a possible or probable event described above and for subjects undergoing total joint replacement for any reason, all images and other source documentation will be provided to the blinded tanezumab Adjudication Committee for review and adjudication of the event. The Adjudication Committee's assessment of the event will represent the final classification of the event (refer to [Appendix 14](#)).

Subjects with adverse event reports of rapidly progressive osteoarthritis (type-1 or type-2), subchondral insufficiency fractures (spontaneous osteonecrosis of the knee [SPONK]), primary osteonecrosis, or pathological fracture, will be withdrawn from treatment and enter the Early Termination Follow-up Period (see [Section 6.9](#)).

The Central Reader will review the Week 24 knee X-rays for evidence of radiographic progression of osteoarthritis. The Central Reader will identify subjects entering the study with asymptomatic knee osteoarthritis Kellgren Lawrence Grade 2 who progress to Kellgren Lawrence Grade ≥ 3 at Week 24. These subjects should be discontinued from tanezumab treatment and entered in the Early Termination Follow-up phase. Unless the Central Reader determines the subject has developed a joint condition that would warrant further evaluation by the Adjudication Committee such as rapidly progressive osteoarthritis, subchondral insufficiency fractures, spontaneous osteonecrosis of the knee (SPONK), primary osteonecrosis or pathological fracture, the images will not be further reviewed by the Adjudication Committee.

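### Protocol 7.4.4 requires a Central Reader X-ray assessment of a joint at risk, but no rule withholds the next SC dose while that X-ray is unread

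*Protocol*

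**What the plan says.** Section 7.4 of the protocol opens by applying its rules at the second and later injections. Within it, Section 7.4.4 places the imaging duty on "Subjects meeting the criteria for increased severe or persistent pain or with other clinically significant findings" in the investigator's assessment. Such a subject has a joint at risk and "must have radiographs (X-rays) of the joint(s) obtained and sent to the Central Reader for assessment". The pain criterion is a score of 7 to 10 in a major joint that lasts at least two weeks despite analgesics.

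Section 7.4.5 acts on the result. It withdraws from treatment "Subjects identified through the measures described above (in Section 7.4.4) who are determined by the Central Reader" to have a possible or probable joint safety event. It also withdraws a subject for whom one of the named joint conditions is reported as an adverse event, without waiting for a read. On timing it says only: "The Central Reader will review the radiology images on an ongoing basis and provide assessments to the investigator and Pfizer".

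Two provisions act on the dosing day. Note a to the Schedule of Activities says that the activities at dosing visits "should be performed prior to dosing with investigational product, unless otherwise noted". Section 7.3.1.2 says: "At each visit, the Investigator will conduct a thorough musculoskeletal physical examination of all major joints".

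**The concern.** The sequence has a trigger (7.4.4) and an outcome (7.4.5) but no instruction for the time between them. If an SC dose falls due after the X-ray is ordered and before it is read, the text neither withholds that dose nor sets a deadline for the read.

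Section 1.2.4.2 gives a higher risk of rapidly progressive osteoarthritis with tanezumab than with placebo or active comparator, based on the Phase 3 osteoarthritis studies. Section 1.2.4.5 lists follow-up of severe persistent joint pain among the measures for managing that risk. A subject under suspicion for this event could therefore receive another dose of a long-acting antibody before the image ordered for that suspicion has been looked at. The issue is patient safety. It does not touch bias, power or any analysis.

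**Working it through.** No figure in the plan needs reproducing here. The check is a count of doses, a comparison of rules and a limited illustration.

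**1. Which doses are tied to a Central Reader read?** There are seven SC doses (Table 4; Sections 6.4.1 to 6.4.9).

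| Dose | Read required before dosing? | Where |
|---|---|---|
| Day 1 | Yes, Screening set | 4.3, 6.1, 7.3.8 |
| Week 8 | No | 6.4.3 |
| Week 16 | No (pain response test only) | 6.4.5 |
| Week 24 | In part, Week 24 set | 6, 6.4.7, 7.3.8 |
| Weeks 32, 40, 48 | No | 6.4.9 |

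Section 7.4 governs 7 − 1 = 6 of these doses. Five have no read requirement. Week 24 is only partly covered: its set includes at-risk joints already identified, but Section 6 allows the films to be taken up to 30 days before the visit. A joint flagged after the films were taken is not on them.

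**2. How does the protocol treat the dose while other questions are open?**

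| Situation | Dose while unresolved |
|---|---|
| Unresolved dysesthesia or allodynia (7.4.1) | SC dose held up to 14 days, then stopped |
| Suspected sympathetic neuropathy (7.4.3) | No SC dose until it is ruled out; limit of 12 weeks from last dose |
| Scheduled Week 24 X-ray (6.4.7) | No SC dose until the reader confirms |
| Triggered X-ray of a joint at risk (7.4.4) | Nothing stated |

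The Week 24 hold applies even to a subject with no joint symptoms. The for-cause X-ray carries none.

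**3. Do the dosing-day checks fill the gap?** No. The joint examination and the review of pain scores come before the dose, so they can identify a joint at risk that day. No text then holds that day's dose.

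**4. What can be said about size?** Read time and trigger rate are not given, so affected doses cannot be counted. As an illustration only, suppose the triggered X-ray falls evenly over an 8-week interval that ends in a dose with no read requirement, and the read takes an assumed r weeks. The read is pending at that dose if the X-ray falls in the last r weeks, a share of r/8:

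- r = 1: 12.5%
- r = 2: 25%
- r = 3: 37.5%

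These are shares of triggered X-rays in such an interval, not of subjects or doses.

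**5. Irreversibility.** Under a simple one-phase decline, the fraction of a dose left after 56 days is 0.5^(56/half-life).

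- Half-life 17 to 24 days (healthy volunteers, 1.2.4.6.1): 0.5^(56/17) = 10.2% to 0.5^(56/24) = 19.8%.
- Half-life 12.5 to 23.5 days (Japanese osteoarthritis subjects, single IV dose, 1.2.4.6.2): 0.5^(56/12.5) = 4.5% to 0.5^(56/23.5) = 19.2%.

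The calculation ignores slow SC absorption (median time to peak 10 to 12 days).

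**The case against.** The strongest reply is that the gap is narrow and the choice defensible.

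- **Low background risk.** In low back pain, Section 1.2.4.2 reports no investigator-reported osteonecrosis or joint replacement in A4091012. In A4091039 it reports one rapidly progressive event, at 20 mg, in a knee with severe osteoarthritis before entry. This trial drops 20 mg and excludes hip Kellgren-Lawrence grade 2 or above, knee grade 3 or above, and symptomatic shoulder osteoarthritis.
- **Existing safeguards.** A merely possible reader call is enough to stop treatment. A named adverse event stops it without a read. Section 6.9 allows withdrawal for safety at any time.
- **A non-specific trigger.** Sections 7.4.1 and 7.4.3 hold on specified adverse events, whereas 7.4.4 reacts to joint pain or any clinically significant finding. Leaving the dose to the investigator is then a reasonable design.
- **Unseen documents.** Section 7.3.8 refers to an imaging Charter and a site imaging manual, which may set a read time or a hold.

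All of this stands as a limit on size and confidence. None of it supplies the missing instruction. A power to withdraw is not a rule to wait, and the adverse-event route needs a diagnosis that the read is meant to provide.

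A reader might also infer that the triggered X-ray is optional, because an earlier paragraph of 7.4.4 asks the investigator to judge "whether more comprehensive evaluation (e.g., radiographic or MRI imaging, orthopedic consultation) of the subject is warranted". The later mandatory wording settles that. The mismatch is editorial and no part of this point.

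**Conclusion.** The point holds on the protocol text: no rule in Sections 7.4.4 or 7.4.5, or in the dosing-visit sections for Weeks 8, 16, 32, 40 and 48, withholds an SC dose while a triggered X-ray is unread. Week 24 is covered only in part. The change is a cheap patient-safety improvement that should be made. The number of affected doses is unknown, the absolute risk is probably low, and the conclusion is subject to whatever the imaging Charter and site manual say.

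Three stronger readings are not supported.

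- **That subjects with an identified joint event would continue dosing.** Section 7.4.5 withdraws them.
- **That about 18% of joint-pain onsets would meet a dose with the read pending.** That figure is 5 × 2/56 = 17.9%. It needs an assumed two-week read, taken from the recommended lead time for the scheduled Week 24 films (7.3.8), and a subject who receives all seven doses. Section 9.1 expects 34% to 54% completers and 42% to 60% responders at Week 16. The factor of 5 also treats Week 24 as fully covered, which errs the other way.
- **That the trial's comparisons are compromised.** Nothing here bears on the analysis, and SAP Section 5.1 plans no formal hypothesis tests.

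**What to change.** Add to Section 7.4.4:

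> When an X-ray of a joint at risk is required under this section, the next SC dose is withheld until the Central Reader has reported no possible or probable joint safety event on that X-ray. If no such report is available by 12 weeks after the last SC dose, the subject receives no further SC doses and enters the Early Termination Follow-up Period (Section 6.9).

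The 12-week limit is the one in 7.4.3 and leaves 12 − 8 = 4 weeks beyond the planned dosing day. Oral product continues, as 7.4.1 and 7.4.3 also hold only the SC dose.

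Costs:

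- A short amendment and site retraining.
- Some late doses. A finding first made on the dosing day delays that dose unless the read is same-day.
- Knock-on delay. Doses must be at least 7 weeks apart and the visit window is ±7 days. After a delay of d weeks, the following dose comes no earlier than d + 7 weeks after the original date, against a window ending at 8 + 1 = 9 weeks. It falls outside its window if d exceeds 2.
- Unequal effect by arm. SC product is placebo in the celecoxib arm, so a hold delays active drug only in the two tanezumab arms. A Week 8 dose held to Day 57 + 28 = 85 leaves Week 12 pain (Days 78 to 84) without a second dose. It could slightly lower Week 12 response or the Week 16 continuation rate in those arms.
- A few lost treatment courses where no clearing read arrives in time, in a study already short of one-year exposures (Section 9.1).

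Data handling is little disturbed. The cap of 12 × 7 = 84 days equals the SAP Section 6.2 diary on-treatment limit. If the previous dose was on target, a dose held for 28 days still lands in its own visit window in SAP Appendix 2.1 (Week 8: Day 85, window 44 to 85; Week 16: 113 + 28 = Day 141, window 86 to 141).
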